
Primary
 
Safety: To determine the safety and reactogenicity of the hAd5-S-Fusion+N-ETSD vaccine at two dose levels for subcutaneous administration, and for sublingual and intranasal dosing.
 
Immunogenicity: To determine immunogenicity of hAd5-S-Fusion+N-ETSD as determined by changes in humoral response.
	
Safety:
 
 • Incidence of MAAEs and SAEs through 1 week post final vaccine administration • Incidence and severity of solicited local reactogenicity AEs through 1 week post final vaccine administration • Incidence and severity of solicited systemic reactogenicity AEs through 1 week post final vaccine administration • Incidence and severity of unsolicited AEs through 1 week post final vaccine administration • Incidence of MAAEs and SAEs through 30 days and 6 months post final vaccine administration • Incidence and severity of unsolicited AEs through 30 days and 6 months post final vaccine administration • Incidence of abnormal changes of laboratory safety examinations • Changes in vital signs 
Immunogenicity: Timing per Schedule of Events
 
 • GMFR in IgG titer to SARS-CoV-2 S, RBD and N. • GMT of S-specific, RBD-specific, and N-specific antibodies against 2019 novel coronavirus tested by ELISA in serum . • Percentage of participants who seroconverted (defined as 4-fold change in antibody titer relative to baseline) . • GMFR in neutralizing antibody .

	
 • GMT of neutralizing antibody . • Seroconversion rate of neutralizing antibody (defined as 4-fold change in antibody titer relative to baseline) .
Secondary	
Safety: 
 • Ascertainment of HIV infections in vaccine recipients through 12 months post final vaccine administration 	Safety: 
 • New HIV infections in vaccine recipients by either two locally approved rapid antibody tests or by ELISA, conducted per Schedule of Events through 12 months post final vaccine administration
Exploratory	

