The Safety Review Committee (SRC), including at least one qualified infectious disease physician independent of the Sponsor and trial reviews safety data.

The SRC will first assess safety when all Cohort 1 participants have completed the toxicity assessment period (defined as 7 days after first vaccine dose, i.e. study day 8). In the absence of safety concerns, enrolment in Cohort 2 will be initiated. The SRC will similarly also assess safety when each of Cohort 2, 3, 4 and 5 participants have completed the toxicity assessment period (defined as 7 days after first vaccine dose, i.e. study day 8). In the absence of safety concerns, enrolment in Cohort 3, 4, 5 and 6 respectively will proceed. Cohorts 3 and 5 will be dosed at 1×10^{11} VP/dose for SC administrations. If safety concerns are identified at the higher dose of 1×10^{11} VP/dose, Cohort 3 and 5 participants will be dosed at 5×10^{10} VP/dose for SC administrations.

All participants will have follow up study visits for the collection of safety, reactogenicity, and/or immunogenicity data at 7 and 14 days after each vaccine dose, 30 days after the last dose, and at 90, 180 and 365 days following the last dose. Additional follow up for safety information will occur via telephone contact as noted in the Schedule of Events.

Safety will be assessed for all participants and will include monitoring of vital signs, and incidence and severity of AEs. Blood samples will be collected for haematology and chemistry analyses and urine samples will be collected for urinalysis. Toxicities will be graded using the Guidance for Industry: Toxicity Grading Scale for Healthy Adult and Adolescent Volunteers Enrolled in Preventive Vaccine Clinical Trials (2007). Solicited local and systemic AEs and unsolicited AEs will be collected using diary cards for 7 days following any dose of vaccine.

Solicited local AEs to be assessed include

Subcutaneous dosing includes injection site:

- Pain,
- Itching,
- Induration,
- Swelling,
- Erythema.

Sublingual dosing include:

- Oral burning,
- Oral swelling,
- Difficulty swallowing,
- Difficulty breathing.

Intranasal dosing include:

- Nasal congestion and coryza
- Epistaxis,
- Pain in the nose,

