
11. HIV positive or other acquired or hereditary immunodeficiency.
 
12. Serious cardiovascular diseases, such as arrhythmia, conduction block, previous myocardial infarction, uncontrolled severe hypertension
 
13. History of hereditary, idiopathic or acquired angioedema.
 
14. Urticaria 12 months prior to screening.
 
15. No spleen or functional asplenia.
 
16. Platelet disorder or other bleeding disorder that may cause injection contraindication.
 
17. Chronic use (more than 14 continuous days) of any medications that may be associated with impaired immune responsiveness including, but not limited to, systemic corticosteroids exceeding 10 mg/day of prednisone equivalent, allergy injections, immunoglobulin, interferon, or immunomodulators. The use of low dose topical, ophthalmic, inhaled and intranasal steroid preparations will be permitted.
 
18. Prior administration of blood products within 120 days before first study vaccination.
 
19. Prior administration of other research medicines or investigational product within 30 days before first study vaccination.
 
20. Prior administration of attenuated vaccine within 30 days before first study vaccination.
 
21. Prior administration of inactivated vaccine within 14 days before first study vaccination.
 
22. Prior administration of SARS-CoV-2 vaccine or likely to receive SARS-CoV-2 vaccination within the upcoming 28 days
 
23. Current treatment with investigational agents for prophylaxis of COVID-19.
 
24. Have a household contact that has been diagnosed with COVID-19 within 14 days before first study vaccination.
 
25. Current anti-tuberculosis prophylaxis or therapy.
 
26. Currently receiving treatment for cancer or history of cancer in the last five years (except basal cell carcinoma of the skin and cervical carcinoma in situ).
 
27. According to the judgement of the investigator any medical, psychiatric, psychological, social, occupational or other conditions that could affect the participants ability to sign informed consent, provide safety assessment data or comply with the requirements of the study protocol.
 
28. Assessed by the Investigator to be unable or unwilling to comply with the requirements of the protocol.
	
Duration of Treatment: Each participant will receive hAd5-S-Fusion+N-ETSD on Day 1. Cohorts 1 & 2 receive a second dose of hAd5-S-Fusion+N-ETSD at Day 22.

--	--

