
Evaluation of Endpoints:
 
Safety: Safety endpoints include assessments of treatment-emergent MAAEs, SAEs, solicited local and systemic reactogenicity AEs, unsolicited AEs, safety laboratory tests, HIV testing and vital signs. Toxicities will be graded using the Guidance for Industry: Toxicity Grading Scale for Healthy Adult and Adolescent Volunteers Enrolled in Preventive Vaccine Clinical Trials (2007).
 
Immunogenicity: GMT of S-specific and N specific antibodies against 2019 novel coronavirus, GMT of neutralizing antibody, and GMT of IgA antibody levels will be evaluated. T cell activity against SARS-CoV-2 S, RBD and N protein will be measured by standard immune assays. Humoral and cellular immunity against the Ad5 vector will be measured at baseline, day 29 and day 181 and 202 (in cohorts 3, 4, 5, 6 and cohorts 1 and 2 respectively) to assess for any induction or enhancement of Ad5 immune responses.
	
Statistical Methods:
 
The purpose of this study is to determine the safety, reactogenicity, and immunogenicity of hAd5-S-Fusion+N-ETSD and select an optimal dose and formulation for future studies. Descriptive statistics will be presented for all study endpoints by individual cohort, pooled by dose level, and for all cohorts combined.
 
Safety will be assessed by the incidence of treatment-emergent MAAEs, SAEs, and solicited local and systemic reactogenicity AEs, and unsolicited AEs for the time period of interest, overall and by grade using the Guidance for Industry: Toxicity Grading Scale for Healthy Adult and Adolescent Volunteers Enrolled in Preventive Vaccine Clinical Trials (2007). Clinically significant changes in safety laboratory tests and vital signs also will be summarized. As suggested by the Ad5 literature and expert opinion, participants will be monitored for incident HIV infection during the follow up period .
 
Immunology analyses will be used to provide an assessment of immune responses. GMFRs and GMTs and their associated 95% confidence intervals (CIs) will be computed by exponentiation of the corresponding log-transformed means and 95% CIs. The percentage of participants who seroconverted (as defined as 4-fold change in antibody titer relative to baseline) and 95% Clopper-Pearson CI will be summarized. Neutralizing antibody levels and CD8+ and CD4+ T-Cell activity also will be summarized.

Figure 1: Study Schema

* In the event of safety concerns participants will be dosed at 5×10^{10} VP/dose

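### Primary safety windows that end at the final dose give unequal exposure when the two-dose and single-dosing-day cohorts are pooled or compared

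*Combined protocol and SAP*

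**What the plan says.** The synopsis table of objectives and endpoints lists the primary safety endpoints. The AE endpoints all end at a time after the last dose: "Incidence of MAAEs and SAEs through 1 week post final vaccine administration", matching 1-week endpoints for solicited and unsolicited AEs, and "Incidence of MAAEs and SAEs through 30 days and 6 months post final vaccine administration", with a matching endpoint for unsolicited AEs. None of them says when the window starts.

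Under Duration of Treatment, "Each participant will receive hAd5-S-Fusion+N-ETSD on Day 1" and "Cohorts 1 & 2 receive a second dose of hAd5-S-Fusion+N-ETSD at Day 22". For Cohorts 3-6, therefore, the first dosing day is also the last. Cohort 5 receives a subcutaneous and a sublingual administration on that one day.

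On collection, Study Design states: "Solicited local and systemic AEs and unsolicited AEs will be collected using diary cards for 7 days following any dose of vaccine". The Schedule of Events also has unsolicited AEs collected by telephone on Day 15 and in the clinic on Day 22 in Cohorts 1-2, so the interval between doses is covered.

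On reporting, Statistical Methods states: "Descriptive statistics will be presented for all study endpoints by individual cohort, pooled by dose level, and for all cohorts combined". AE incidence is to be given "for the time period of interest", which is not defined further. The synopsis and Schedule of Events describe no per-dose table and no exposure-adjusted rate.

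**The concern.** A proportion of participants with at least one event rises with the number of doses and the days observed. If some participants contribute two doses and four weeks and others one dosing day and one week, a single pooled proportion describes neither regimen.

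This matters most for the summary by dose level, because the trial is meant to select a dose. As planned, the 5×10^10 VP level is Cohort 1 alone, where everyone is due two doses. The 1×10^11 VP level combines Cohort 2 (two doses) with cohorts dosed on one day. Dose level is therefore confounded with number of doses, and the lower level is favoured with the longer exposure. A reader of that table could miss a real dose-level difference, or see one in the wrong direction. The same applies to any contrast across the two groups, such as Cohort 2 against Cohort 3, which share dose and route but not the number of doses.

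**Working it through.** **Check on the calendar.** Study day = day of final dose + days after it. For 180 days this gives 1 + 180 = 181 and 22 + 180 = 202, which are the days the exploratory endpoints state for Cohorts 3-6 and Cohorts 1-2. For 7 days it gives Days 8 and 29, and for 30 days Days 31 and 52, matching the Schedule of Events. (Later Cohort 1-2 entries in its Study Day row do not follow this rule. That may be a fault of text conversion, and nothing here uses them.)

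**Window lengths**, read cumulatively from Day 1, elapsed days = study day − 1, at nominal visit days:

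| Window after final dose | Cohorts 1-2 | Cohorts 3-6 | Ratio |
|---|---|---|---|
| 1 week (unsolicited AEs, MAAEs, SAEs) | 29 − 1 = 28 | 8 − 1 = 7 | 4.0 |
| 1 week (solicited, diary days) | 2 × 7 = 14 | 7 | 2.0 |
| 30 days | 52 − 1 = 51 | 31 − 1 = 30 | 1.7 |
| 6 months (180 days) | 202 − 1 = 201 | 181 − 1 = 180 | 1.12 |

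**Weight in the pools, 1-week window.** Over all 60 participants, Cohorts 1-2 supply 20 × 28 = 560 person-days and Cohorts 3-6 supply 40 × 7 = 280. One third of participants give 560/840 = 67% of the exposure. In a 1×10^11 VP pool of Cohorts 2, 3 and 4, Cohort 2 gives 280/(280 + 140) = 67%. If Cohort 5 is included, it gives 280/490 = 57%.

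**Illustration for solicited reactions.** The documents give no reaction rates, so the per-dose risk p is an assumption. With independent doses, two-dose incidence is 1 − (1 − p)². With no dose-level effect:

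| p (assumed) | 5×10^10 VP: Cohort 1 | 1×10^11 VP: Cohorts 2, 3, 4 | Gap, points |
|---|---|---|---|
| 10% | 19% | (19 + 10 + 10)/3 = 13% | 6 |
| 30% | 51% | (51 + 30 + 30)/3 = 37% | 14 |
| 50% | 75% | (75 + 50 + 50)/3 = 58% | 17 |

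If instead the higher level truly carried 40% per dose against 30%, Cohort 2 would show 1 − 0.6² = 64% and the pool (64 + 40 + 40)/3 = 48%. That is still below 51%, so the order is reversed. In the 7 days after dose 1, the same assumptions give 30% against 40%, in the right order.

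**Illustration for unsolicited AEs.** With an assumed constant background risk of 2%, 5% or 10% per week, Cohorts 3-6 show 2%, 5% or 10% over one week. Cohorts 1-2 show 1 − 0.98⁴ = 7.8%, 1 − 0.95⁴ = 18.5% or 1 − 0.90⁴ = 34% over four weeks, with no vaccine difference.

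**The other reading.** If only the week after the final dose is meant, the windows are 7 against 7 days. Reactions to dose 1 in the 20 participants of Cohorts 1-2 then drop out of the 1-week endpoints.

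**The case against.** A reader might infer that the comparison of routes is biased, with two-dose subcutaneous cohorts set against sublingual or intranasal ones. The documents do not support that. Study Design places the route comparison within Cohorts 3-6, whose subcutaneous arm is Cohort 3, and all four are dosed on Day 1 only. The subcutaneous dose-level comparison is available as Cohort 1 against Cohort 2, both two-dose. Results are also to be shown for each cohort separately, which preserves both comparisons.

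Other fair points are that the analysis is descriptive with no between-cohort test, that the fourfold ratio applies only to the 1-week windows for unsolicited AEs, MAAEs and SAEs, and that a cumulative incidence for a whole regimen is a legitimate summary. The rates above are assumed. Positive correlation between a participant's responses to the two doses would shrink the 51% towards 30%, and with it the gap. The samples are also small: 5 of 10 has a 95% Clopper-Pearson interval of 19% to 81%. Nor would equal windows make the pools homogeneous, since Cohorts 1-2 are seronegative, Cohorts 3-6 seropositive, and the solicited local items differ by route.

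These points limit the concern to pooled and cross-group summaries. They do not remove it there. The by-dose-level table is planned, its two levels differ in number of doses by design, and nothing in the synopsis or Schedule of Events tells the analyst to separate doses.

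**Conclusion.** The concern holds for the summaries pooled by dose level, for the all-cohort totals, and for contrasts between Cohorts 1-2 and Cohorts 3-6. It does not hold within either group. The window lengths follow from the documents on the cumulative reading, which is the likelier one but is inferred, because no start is stated. The alternative reading equalises the windows at the price of losing dose 1 reactions, so the wording needs attention either way.

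The 14-point gap (51% against 37%) is an illustration. It assumes 30% risk per dose, independent doses and a 1×10^11 VP pool of Cohorts 2, 3 and 4. Its direction holds whenever dose 2 produces any first reactions. Use of the dose fallback for safety concerns would change which cohorts make up each level.

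Three stronger readings go too far. Calling the pooling invalid is too strong for descriptive tables, which are hard to interpret as planned but can be repaired. Saying that dose 2 effects are lost is also too strong: diaries are issued at each dose and collected separately on Days 8 and 29, so the data exist and only the tabulation is missing. Finally, a window that depends on outcome, through a participant who stops after dose 1, is a possibility and not a stated rule, because the documents do not define the final dose for that case.

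**What to change.** Amend the endpoint wording and the Statistical Methods as follows.

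- State that each window starts at a dose actually received. This also settles the case of a participant who does not receive dose 2.
- Tabulate by dose number the solicited AEs, and the unsolicited AEs, MAAEs and SAEs within 7 days of a dose.
- For summaries by dose level, over all cohorts, or across the two groups, use the 7 days after dose 1. The Safety Review Committee already reviews this window (Day 8), and it is the same length in all six cohorts.
- Keep the cumulative 30-day and 6-month incidences by cohort, and add rates per person-time wherever they are pooled.
- Do not use a 30-day post-dose-1 window cut off at dose 2 for cross-group comparison. It would be 22 − 1 = 21 days in Cohorts 1-2 against 30 in Cohorts 3-6.
- Label pooled rates as mixing serostatus and route, which this change does not remove.

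No new data are needed. The cost is the revised wording and a few extra tables.

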To avoid the adenovirus (Ad) immunization barrier for first generation Ad5 [E1-, E3-] vectors, the 2nd-generation hAd5 vector has two additional deletions in the E2b region, removing the DNA polymerase and the preterminal protein genes (E1-, E2b-, E3-). Deletion of the E2b region confers advantageous immune properties on the novel hAd5 vectors, eliciting potent immune responses to inserted antigens while minimizing the immune responses to Ad5 proteins. Thus, the hAd5 [E1-, E2b-, E3-] vector overcomes limitations of early generation vectors, as it permits the immunization of people who have been previously exposed to Ad5. Further, overcoming this vector induced immune responses thought to contribute to increased HIV acquisition risk makes the candidate feasible for testing in high HIV prevalence settings. We believe that hAd5 [E1-, E2b-, E3-] vectors are likely superior to Ad5 [E1-, E3-] vectors in immunogenicity and safety and are the best platform to develop a COVID-19 vaccine in a rapid and efficient manner.

To date, the majority of vaccine strategies in development involve developing immunogenicity against S protein. However, recent evidence in patients who recovered from COVID-19 demonstrates Th1 immunity generated against N protein ([Grifoni 2020](#)). A second report by Grifoni et al. further confirmed that in the predictive bioinformatics model, T and B cell epitopes were highest for both S and N ([Grifoni 2020b](#)).

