^a Day 1 chemistry, haematology, and urinalysis assessments do not need to be repeated if screening assessments were performed within 7 days prior to the first study vaccination; ^b Height required at screening visit only; ^c Vital signs of temperature, heart rate, blood pressure, and respiratory rate will be assessed at every visit. Temperature will be documented at each visit and subsequently if clinically indicated; ^d See Table 12 or additional details on laboratory assessments. Blood draws for lab assessments at vaccination visits should occur prior to vaccine administration; ^e Haematology to include FBC with differential (5 part) as outlined in Table 12. Blood draws for lab assessments at vaccination visits should occur prior to vaccine administration; ^f Urinalysis testing will include at a minimum protein, glucose, and presence of red blood cells. Sample collection at vaccination visits should occur prior to vaccine administration; ^g Immunogenicity testing includes measures of antibody response and cell-mediated immunity against target antigens, as well as hAd5 serostatus for determining baseline, day 29 and day 181 and 202(in cohorts 3, 4, 5, 6 and cohorts 1 and 2 respectively) hAd5 immunity and monitoring for anti-vector immune responses. Sample collection at vaccination visits should occur prior to vaccine administration.

^h Serum or urine pregnancy tests for females of child-bearing potential at baseline/screening and each visit where study drug is administered, and at 30 days post last dose of vaccine; ⁱ Complete physical exam at screening visit. A routine symptom directed physical exam at subsequent visits; ^j Assessment of reactogenicity AEs includes a baseline assessment of the injection site and any signs or symptoms that may overlap with reactogenicity, as well as an assessment of immediate reactogenicity AEs 30 minutes after vaccine administration; ^k HIV pre- and post-test counselling are done at each visits where blood is taken for HIV testing; ^l Tuberculosis Screening per local guidelines

☺ = In-person visit; ☎ = Telephonic follow-up

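### Solicited reactions in the two-dose cohorts are counted in one cumulative window and pooled by dose level with single-dose cohorts, and no paired interval is planned for the titre change after dose 2

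*Combined protocol and SAP*

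**What the plan says.** Under Duration of Treatment, "Cohorts 1 & 2 receive a second dose of hAd5-S-Fusion+N-ETSD at Day 22". The cohort table in Study Design gives Cohorts 3 to 6 a single dosing day.

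For reactogenicity, the primary endpoint is "Incidence and severity of solicited local reactogenicity AEs through 1 week post final vaccine administration", and the systemic endpoint uses the same window. Study Design has solicited events recorded on diary cards for a week after each dose. In Table 9 (Cohorts 1 & 2), cards are issued on Days 1 and 22 and collected on Days 8 and 29. Statistical Methods summarises every endpoint per cohort, per dose level and across all cohorts. Dose number is not among the groupings.

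For antibody response, the primary endpoints include "GMFR in IgG titer to SARS-CoV-2 S, RBD and N", with no reference visit named, and "GMT of S-specific, RBD-specific, and N-specific antibodies against 2019 novel coronavirus tested by ELISA in serum", which is a level and needs none. Only seroconversion is tied to baseline: "Percentage of participants who seroconverted (defined as 4-fold change in antibody titer relative to baseline". On intervals, "GMFRs and GMTs and their associated 95% confidence intervals (CIs) will be computed by exponentiation of the corresponding log-transformed means" and the matching log-scale limits. Table 9 schedules immunogenicity samples for Cohorts 1 and 2 on Days 1, 8, 22, 29 and 52, among others. Footnote g adds: "Sample collection at vaccination visits should occur prior to vaccine administration". A pre-dose-2 value on Day 22 should therefore exist for each participant who attends.

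**The concern.** Reactogenicity at two subcutaneous dose levels is part of the primary objective, and the trial is meant to inform dose selection. A cumulative percentage depends on how many doses a person had a chance to react to. As planned, the lower subcutaneous level consists only of Cohort 1, where everyone has two doses. The 1×10^11 VP level contains two-dose Cohort 2 together with single-dose cohorts. A difference between the pooled levels can therefore reflect the number of doses and not the dose level. The cumulative rate also cannot show whether reactions become more or less frequent on the second exposure.

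The titre side is a smaller gap of the same kind. The design provides a sample just before dose 2 and samples 7 and 30 days after it, but no stated analysis uses Day 22 as a reference. A reader who wants to know how far titres move after dose 2, and how precisely that is known, has only separate visit-wise intervals.

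**Working it through.** The documents give no SD, correlation, expected reaction rate or sample-size derivation, so there is no planned figure to reproduce. From the documents: 10 participants per cohort, dosing days, sampling days, diary days. Assumed: everything marked as such below.

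**1. Cumulative reaction risk.** Let p1 and p2 be the per-dose risks. With independent reactions, the cumulative risk is 1 − (1 − p1)(1 − p2). With full positive dependence it is max(p1, p2).

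| Assumed p1, p2 | Full dependence | Independence | Single dose (p1) |
|---|---|---|---|
| 20%, 20% | 20% | 1 − 0.8 × 0.8 = 36% | 20% |
| 10%, 30% | 30% | 1 − 0.9 × 0.7 = 37% | 10% |
| 30%, 10% | 30% | 1 − 0.7 × 0.9 = 37% | 30% |

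The last two rows have opposite patterns over the two doses and the same cumulative rate.

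**2. Effect on pooled dose levels.** Take a 20% risk at every dose, whatever the level, so there is no dose effect at all.
- Lower level, Cohort 1 alone: 20% to 36%.
- 1×10^11 VP level from Cohorts 2 and 3: 20% under full dependence, (36% + 20%)/2 = 28% under independence.
- The same level with Cohort 4 added (systemic events only, since the local event list differs by route): 20%, or (36% + 20% + 20%)/3 = 25.3%.

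The lower level can thus look more reactogenic by 0 to 8 points (36 − 28), or 0 to 10.7 points with Cohort 4, with no true difference. Cohort 5 is left out because the plan does not say to which level its combined administration belongs.

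**3. What a cumulative count says about dose 2.** If 8 of 10 participants react at some point over both doses, the number reacting after dose 2 can be anything from 0 to 8. Tabulated by dose, a count such as 2/10 after dose 2 would have a 95% Clopper-Pearson interval of 2.5% to 55.6%.

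**4. Titre: point estimate.** On the log scale, the mean of (Day 52 − Day 22) equals the mean at Day 52 minus the mean at Day 22 when the same people contribute to both. The ratio of the two visit GMTs is then exactly the paired fold rise; in a numerical check both routes gave 2.618. The planned visit-wise summaries therefore already imply the point estimate.

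**5. Titre: interval.** Assume the same log10 SD, s, at both visits and within-person correlation ρ. The 95% limits are the estimate multiplied and divided by:
- paired: 10^[t(0.975; 9) × s × √(2(1 − ρ)) / √10]
- treated as independent: 10^[t(0.975; 18) × s × √(2/10)]

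With s = 0.5 and ρ = 0.7:
- paired: 2.262 × 0.5 × √0.6 / √10 = 0.277, a factor of 1.89
- independent: 2.101 × 0.5 × √0.2 = 0.470, a factor of 2.95

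Over s = 0.4 to 0.6 and ρ = 0.5 to 0.7, the paired factor runs from 1.67 to 2.69 and the independent one from 2.4 to 3.7. Visit-wise intervals reveal s but not ρ between Day 22 and the later visit. Fold rises from Day 1 do not supply it either, because they carry only correlations with Day 1.

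**The case against.** The strongest reply is that the plan is descriptive, states no objective about the increment from dose 2, and collects everything needed. Diaries are issued and collected separately, the adverse-event summary is for an unspecified period of interest, and a by-dose table is not excluded. Tables for individual cohorts are also planned, and Cohort 1 against Cohort 2 compares two levels with the same number of doses. All of this stands. It makes the gap one of analysis specification and not of data, and confines the distortion to pooled summaries and to comparisons between two-dose and single-dose cohorts. It does not remove the gap, because pooling by dose level is stated and a by-dose table is not.

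Several stronger readings are tempting and are not supported:
- A reader might infer that every response is measured from Day 1. Only seroconversion is; the fold rise names no reference and the GMT needs none.
- A reader might infer that the two diaries are merged. The text does not say so; it follows only from the wording of the endpoint window.
- A reader might conclude that there is no estimate of the change in titre after dose 2. With complete data the visit GMTs imply one; only its interval is missing.
- A reader might treat 36% as the cumulative rate. It requires independent reactions to the two doses; positive dependence brings it down towards 20%.

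Finally, the text available reads like a synopsis, so what is said here to be absent is absent from that text.

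**Conclusion.** The point holds as a gap in the analysis specification. For solicited events, following the plan gives a cumulative two-dose rate that is pooled by dose level with single-dose rates. At an assumed 20% risk per dose, the two-dose rate is 20% to 36% against 20%, and a pooled comparison of subcutaneous levels can show a spurious difference of 0 to 8 points. These ranges assume non-negative within-person dependence and equal per-dose risk.

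For titre, the missing item is the paired interval. Its factor is about 1.9 with 10 participants at the assumed SD and correlation, against 2.95 if the visits are treated as independent.

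One further inference should be avoided. The vector rationale says that "it permits the immunization of people who have been previously exposed to Ad5", and the rise after Day 22 may look like a within-person test of this, or like the isolated effect of dose 2. It is neither. The response to dose 1 may still be rising at Day 22, both seronegative cohorts receive two doses, and the single-dose cohorts are seropositive, so nothing in the trial separates the two. The ratio describes change after dose 2.

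**What to change.** In Statistical Methods:

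1. Tabulate solicited local and systemic events separately for the 7 days after dose 1 and the 7 days after dose 2. Use the per-dose tables when comparing or pooling across cohorts and dose levels, with dose 1 as the basis for any comparison with single-dose cohorts. Keep the cumulative endpoint as it is.
2. State that the fold rise is relative to Day 1. For participants in Cohorts 1 and 2 who received both doses, add the paired fold rise with 95% CI of Day 29 and of Day 52 over the pre-dose Day 22 sample, for S, RBD and N IgG and for neutralising antibody. Label it as change after dose 2, and say that it is not that dose's isolated effect because there is no single-dose seronegative cohort.

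The cost is a few sentences and a few tables. The titre part adds 4 analytes × 2 visits × 2 cohorts = 16 descriptive intervals. No new sample, assay, visit or participant is needed.
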